#### 5.5 Strategies for Recruitment and Retention

Potential patients with advanced HCC will be identified in the multidisciplinary liver cancer programs at the participating sites. This may include review during multidisciplinary tumor boards to identify potential participating patients. Potential participating patients will be referred in to the site cancer center ambulatory clinics for formal screening and consent. It is anticipated that 90 patients total may need to be screened anticipating potential screening failures. The study title will be included on cancer center web content listing available clinical trials at individual study site. The study will also be listed on https://clinicaltrials.gov website.

The inclusion and exclusion criteria in this study should not have a negative effect on the enrollment of the desired populations.

Target enrollment for this study is 50 patients over 2 years. The target accrual goal is 25 patients per year. Patients will be recruited from physicians participating in this study. Consenting, screening, and treatment will take place at the NYU Langone Health PCC or participating sub-sites under the supervision of the Site PI. Prospective subjects will receive detailed information regarding this study; its investigational nature, required study procedures, alternative treatments, risks and potential benefits of the study. They will also receive the informed consent document to read. All questions are answered by the PI and qualified research personnel.

The Principal Investigator will:

- 1. Obtain signed and dated informed consent from the potential subject before any study specific procedures are performed.
- 2. Determine patient eligibility; see Section 5.1 and 5.2
- 3. Submit registration to NYU Langone Health Perlmutter Cancer Center CTO
- 4. Receive registration confirmation from the NYU Langone Health Perlmutter Cancer Center CTO, including a unique study identification number assigned to the patient that will be distributed to the study team upon registration of the patient.

The informed consent process and documentation follows established institutional guidelines.

#### 5.6 Registration Procedures

#### 5.6.1 General Guidelines

Each patient must sign and date an informed consent form before undergoing any study specific procedure unless a procedure is being performed as part of the patient's standard of care.

Version: 11.0

Enrollment in the study requires that all inclusion and exclusion criteria have been met. Enrollment occurs upon confirmation of registration from the NYULH PCC Clinical Trials Office. The following materials must be submitted to the CTO for subject registration:

- 1. Complete signed and dated informed consent form
- 2. Complete signed and dated eligibility checklist
- 3. All supporting documentation verifying each eligibility criterion has been met

Registration will occur within 48 hours of research coordinator receipt of all of the above documents. A written confirmation of enrollment including a unique study identification number assigned by the research coordinator will be disbursed to the study team upon registration.

A unique patient study number will be issued once consent is received, due to serum IL-8 samples collected prior to eligibility confirmation. The patient will not be identified by name. Once remaining registration material is verified, the patient is considered accrued on study.

#### 5.6.2 Multi-Site Surveillance

As the lead investigator in a multi-site trial, the Principal Investigator is responsible for organizing and conducting monthly teleconferences with all participating sites. The PI will also be responsible for including data from all of the participating sites within the overall trial's quarterly Data and Safety Monitoring report to the DSMC. Each participating site will be responsible for submitting the results and recommendations from the DSMC's quarterly reviews to their IRB of record at the time of continuing review. Additionally, the NYU Langone Health PCC Clinical Trial Office, Quality Assurance Unit will provide remote extensive monitoring including real-time review of all eCRFs to ensure completeness and compliance with the protocol (100% source documentation verification). Additionally, a first subject audit is to be completed within four weeks of enrollment.

#### 5.6.3 Patient Registration at Additional Sites

Enrollment at addition sites can begin once each site's IRB has approved this protocol, a copy of each site's IRB approval, Citi training certificates, Medical Licenses and signed CVs are provided to NYU Langone Health Perlmutter Cancer Center (PCC) Clinical Trials Office. Once, all required documents are provided to NYU Clinical Trials Office an activation notification will be sent to the PI and research coordinator of that site. Central registration for this study will take place at NYU Langone Health PCC Quality Assurance Unit ([contact]).

Each patient must sign and date an informed consent form before undergoing any study specific procedures unless a procedure is being performed as part of the patient's standard of care. Once a patient has signed consent, each site must notify the NYU Langone Health PCC Quality Assurance Unit and forward a copy of the signed consent to NYU Langone Health PCC Clinical Trials Office within 24 hours.

Enrollment in the study requires that all inclusion and exclusion criteria have been met. Enrollment occurs upon confirmation of registration from the NYU Langone Health PCC Clinical Trials Office. The following materials must be submitted to the Quality Assurance Unit at NYU Langone Health via email ([contact]):

- 1. Complete signed and dated informed consent form
- 2. Complete signed and dated informed consent checklist
- 3. Complete signed and dated eligibility checklist
- 4. All supporting documentation verifying each criterion has been met.

Registration will occur once the Senior Research Nurse for Quality Assurance conducts a central review of the submitted materials. A unique patient study number will be issued once consent is received, due to serum IL-8 samples collected prior to eligibility confirmation. The NYU Langone Health

Version: 11.0

PCC CTO will provide the subject's unique study number via email. Once remaining registration material is verified a signed eligibility conformation worksheet email is sent. This number is unique to the participant and must be written on all data and correspondence for the participant.

The subject will not be identified by name. This is the point, at which, the patient is considered accrued on study. Protocol treatment should begin within designated timeframe; issues that would cause treatment delays should be discussed with the overall PI, [name]. All screen failures/ineligible subjects, as well as subject's who withdraw consent prior to initiation of protocol therapy must be submitted to the CTO in a manner analogous to the procedures noted above. Applicable source documentation will be required within the corresponding submissions.

Subjects must not start any protocol procedures prior to registration; each participating institution will order the study agent directly from the supplier, Bristol-Myers Squibb (Nivolumab, BMS-986253).

Each site is responsible for reporting all unexpected problems involving risks to participants or others to NYU Langone Health PCC Clinical Trials Office and to their IRB as per site institutional policy.

Please email all SAEs to [contact], [name], PCC Assigned Medical Monitor, and the NYU Langone Health CTO Quality Assurance specialist.

#### 5.7 Duration of Study Participation

Study participants will receive study drug until events such as (outlined in Section 5.9.1) a) disease progression, b) treatment related toxicity or other adverse event preventing continued participation, or c) withdrawal of consent. It is estimated that of the 50 enrolled, evaluable patients, that 50% will complete 17 cycles and 50% will complete an additional 17 cycles. Thus, the screening period and intervention period for 50% of participants will have a duration of 17.5 months and for 50% a duration of 34.5 months. The follow up period will occur for at least every 3 months for 1 year after last study treatment dosage, even in patients who discontinue the study drug. Thus the total study duration is estimated to be 20.5-23.5 months for 50% of participants and 34.5-37.5 months for 50% of participants.

#### 5.8 Total Number of Participants and Sites

Recruitment will end when approximately 50 participants are randomized over 2 years. It is expected that approximately 70 participants will be screened in order to enroll and produce 50 randomized participants. There will be no international sites. Other U.S. sites may be considered to facilitate enrollment.

#### 5.9 Participant Withdrawal or Termination

#### 5.9.1 Reasons for Withdrawal or Termination

Participants are free to withdraw from participation in the study at any time upon request. An investigator may terminate participation in the study if:

- Any clinical adverse event (AE), laboratory abnormality, or other medical condition or situation
  occurs such that continued participation in the study would not be in the best interest of the
  participant
- The participant meets an exclusion criterion (either newly developed or not previously recognized) that precludes further study participation

Version: 11.0

A subject has the right to voluntarily discontinue study treatment or withdraw from the study at any time, for any reason, and without repercussion. The investigator and supporter have the right to discontinue a patient from study treatment or withdraw a patient from the study at any time.

Reasons for subject withdrawal from the study may include, but are not limited to:

- Subject withdrawal of consent at any time.
- Disease progression (if applicable)
- Intolerable toxicity (If applicable)
- Any medical condition that the investigator or supporter determines may jeopardize the patient's safety if s/he continues in the study or continues treatment with study drug.
- The investigator or supporter determines it is in the best interest of the patient.
- Failure of the subject to adhere to protocol procedure requirements
- Pregnancy (if applicable)
- Study termination by Supporter

The reason for taking a participant off study, and the date the participant was removed, must be documented in the case report form (CRF). All patients who withdraw from study drug prematurely will undergo end-of-treatment assessments within 30 days after the last dose, if possible. Regardless of the reason for withdrawal, effort shall be made to follow safety events from the time of withdrawal through resolution or until the event stabilizes. Subjects who discontinue study drugs will continue to be followed for adverse events for up to 100 days and for survival every 3 months (+/- 2 weeks) from the date of last dose of study drug(s) for up to 12 months.

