#### 5.9.2 Handling of Participant Withdrawals or Termination

Significant efforts will be made to continue follow-up of withdrawn or terminated participants or participants who discontinue study agent but remain in the study for follow-up, especially for safety and efficacy of secondary study endpoints. Every effort will be made to undertake protocol-specified safety follow-up procedures to capture AEs, serious adverse events (SAEs), and unanticipated problems (UPs). The PI and site PIs will attempt to obtain at a minimum survival data on all participants lost to follow-up. Methods that will be used prior to stating that a participant is lost to follow up will include at least three phone calls to participant or next-of-kin if possible. A certified letter will be mailed if the phone calls fail to secure follow up information.

Withdrawal from the study can be made in writing to the Principal Investigator, [name]. Any samples/specimens remaining after formal withdrawal, will be destroyed/discarded per Institutional guidelines.

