#### 7.3.4 Final Study Visit

A final study visit will be scheduled if a treatment related or non-treatment related AE occurs such that further treatment is not advised, disease progression has occurred, or participant wishes to withdraw from the study (or other reasons as listed in Section 5.9).

For participants having suspected disease progression, consideration will be made for ultrasound or CT guided tumor biopsy as part of standard of care. For participants deemed to be deriving a clinical benefit despite evidence of disease progression, consideration will be made for continuation of study drug treatment. For example, appearance of new tumors if index tumors have had a response/stable disease will be one type of consideration. If tissue biopsy is obtained, clinical and translational core biopsy tissue will be obtained and processed as described (Section 7.2). Study participants will be informed regarding all results of diagnostic imaging studies and clinical pathology biopsy results.

- In order to allow continued administration of study treatment despite progression of disease, e.g. based on appearance of a new lesion, patients must have absence of symptoms and signs of clinically important morbidity due to disease progression (e.g. requirement for additional medical management to control symptoms or irradiations to prevent morbidity), absence of symptomatic rapid disease progression requiring urgent medical intervention (e.g. spinal cord compression), and no decline in ECOG or Karnofsky performance status
- If a patient is treated past disease progression, the patient will be re-consented using a written informed consent document at that time.
- Patients treated past disease progression will then be re-evaluated at 3 month intervals with CT or MRI to determine if progression is confirmed.

If there are any ongoing AEs or SAEs, participants will continue to receive treatment and follow up as per standard of care. Documentation of resolution or continued progression of AEs/SAEs will be provided.

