### 7.3.5 Withdrawal/Early Termination Visit

Significant efforts will be made to continue follow-up of withdrawn or terminated participants or participants who discontinue study agent but remain in the study for follow-up, especially for safety and efficacy of secondary study endpoints. Every effort will be made to undertake protocol-specified safety follow-up procedures to capture AEs, serious adverse events (SAEs), and unanticipated problems (UPs). Subjects whom do not wish to continue further follow-up can formally withdraw consent, having the below assessments obtained. The PI and site PIs will attempt to obtain at a minimum survival data on all participants lost to follow-up. Methods that will be used prior to stating that a participant is lost to follow up will include at least three phone calls to participant or next-of-kin if possible. A certified letter will be mailed if the phone calls fail to secure follow up information.

- Record adverse events as reported by participant or observed by investigator.
- Record vital signs, results of medical history, physical exam, height/weight, performance status (ECOG).
- Collect blood for hematology, biochemistry, coagulation (Section 7.2.1), AFP
- MRI abdomen (or CT if not eligible), 3 phase IV contrast, liver protocol if greater than 6 weeks since most recent evaluation radiographic evaluation
- Tumor objective response determination (RECIST v. 1.1).
- Provide final instructions to participant with regard to management of AEs.

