### 7.3.7 Follow-Up Visits

The follow-up period will occur for at least every 3 months for 1 year after last study treatment dosage, even in patients who discontinue the study drug.

- Record survival status
- Record adverse events and concomitant medications as reported by participant or observed by investigator.
- Record vital signs, results of medical history, physical exam, height/weight, performance status (ECOG).
- Collect blood for hematology, biochemistry, coagulation (Section 7.2.1), AFP
- Record new anti-cancer treatment since last study visit, if applicable
- MRI abdomen (or CT if not eligible), 3 phase IV contrast, liver protocol.
- CT chest (with or without IV contrast).

Version: 11.0

Tumor objective response determination (RECIST v. 1.1).

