# 10 Statistical Considerations

# 10.1 Statistical and Analytical Plans (SAP)

A formal SAP will be completed prior to database lock.

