# 20 Schedule of Events

STUDY DAY	Prestudy, screening  (Day -20 to -1)	C1D1	(+/- 3 days)	C2D1 (Day 29+/- 3 days)	C2D15 (Day 45+/- 3 days)	C3D1 (Day 59+/- 3 days)	C3D15 (Day 74+/- 3 days)	Subsequent Visits* (Estimate 24 visits average)	Follow Up F
Study Team Procedures									
Informed Consent	Х								
Medical History	Х		Х	Х	Х	Х	Х	Х	Х
Physical Exam	Χ		Х	Х	Х	Х	Х	X	Х
Vital Signs	Х		Х						Х
Weight	Х		Х	Х	Х	Х	X	Х	Х
Height	Х								Х
ECOG Performance Status	Х		X	X	Х	X	Х	X	Х
Toxicity Evaluations (AE reporting)		Х	Х	Х	Х	Х	Х	Х	Х
Concomitant Medications	Х	Х	X	Х	Х	Х	Х	Х	Х
RECIST v. 1.1 A	Х					Х		Х	X F
Study Drugs B		Х	Х	Х	Х	Х	Х	Х	
Venipuncture	Х	Х	Х	Х	Х	Χ	Х	Х	
Laboratory Assessments									
CBC, CMP, INR	Х	Х	Х	Х	Х	Х	Х	Х	Х

Version: 11.0

AFP C	Х					Х		Х	X F
TSH Testing	Х	X		X		X		X	
Venipuncture	Х	Х	Х	Х	Х	Х	X	X	Х
Serum Pregnancy Test		Х							
Translational Peripheral Blood Sample D	X					X			
Tumor Biopsy	Х					Х			
Fresh frozen tissue from core biopsy (Processing)	X					Х			
Imaging Assessments									
Imaging E	Х					Х		Х	X F

A every 8 weeks for 12 months, see Schema

B Arm 1: Nivolumab 240 mg IV every 2 weeks; Arm 2: BMS-986253 2400mg IV + Nivolumab 240mg IV every 2 weeks; C AFP to be checked pre-study and at every 8 weeks for 12 months, see Schema IL-8 level and other, cycle 3 only E 3-phase liver CT, or MR abdomen with contrast every 8 weeks for 12 months, see Schema

F every 3 months for 1 year, See Schema
\*Scheduled treatment visits occurring after Cycle3

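### Scheduled survival contact ends about 12 months after last dose, so later deaths are not systematically collected: OS loses events, and its curve after month 12 may read too high by an unknown amount

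*Combined protocol and SAP*

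**What the plan says.** - **Window.** Section 5.9.1 follows those who stop drug "for survival every 3 months (+/- 2 weeks) from the date of last dose of study drug(s) for up to 12 months". Section 7.3.7 says "The follow-up period will occur for at least every 3 months for 1 year after last study treatment dosage", and section 5.7 is worded almost identically. The follow-up footnote in section 20 also gives one year and refers to a schema that is not visible in the text.
- **What starts the clock.** Under section 5.7, drug continues until progression, toxicity or withdrawal of consent. Section 7.3.4 allows treatment past progression in selected cases ("consideration will be made for continuation of study drug treatment").
- **Expected time on drug.** Section 5.7 estimates that "50% will complete 17 cycles and 50% will complete an additional 17 cycles". Section 20 puts the visits after cycle 3 at "Estimate 24 visits average".
- **Other routes to late deaths.** Under section 5.9.2 the investigators "will attempt to obtain at a minimum survival data on all participants lost to follow-up". Section 7.3.5 promises continued efforts, "especially for safety and efficacy of secondary study endpoints". Section 8.3 asks for notification of a death after participation ends, but only where it may reasonably be related to the study.
- **Analysis.** OS is secondary. It is analysed by Kaplan-Meier and log-rank (section 10.4.3) in all randomised participants (section 10.3). No OS censoring rule or common cut-off is given, and section 10.1 says "A formal SAP will be completed prior to database lock".

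**The concern.** A living participant who progresses and stops early leaves OS follow-up sooner than one who stays on drug. The protocol's own background figures (section 2.2.2) show how prognostic this is: median OS by best response was not reached for responders, 16.7 months for stable disease (SD) and 8.9 months for progressive disease (PD). Two things follow.

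1. Deaths after the window are not systematically recorded, so OS has fewer events and less precision.
2. Participants with poorer prognosis can be censored first. Kaplan-Meier assumes that censoring is unrelated to prognosis, so the curve can sit too high after the first such censoring.

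Someone randomised but never treated (section 10.6) is in the analysis set but has no last dose, so no survival clock is defined for them. The documents give no number for this group, and it adds nothing to the estimates below.

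**Working it through.** **1. The plan's own durations.** The documents give no OS event count, power or bias figure, so the check starts from section 5.7. A cycle is 4 weeks (section 6.1.8).
- 17 × 28/30.44 = 15.6 months and 34 × 28/30.44 = 31.3 months on drug.
- Adding 12 gives 27.6 and 43.3 months. On this reading the window censors no survivor before month 27.6.

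Section 5.7 also states screening plus treatment of 17.5 and 34.5 months, and total durations of 20.5–23.5 and 34.5–37.5 months.
- Implied follow-up: 20.5 − 17.5 = 3 to 23.5 − 17.5 = 6 months, and 34.5 − 34.5 = 0 to 37.5 − 34.5 = 3 months.
- With a full year the totals would be 17.5 + 12 = 29.5 and 34.5 + 12 = 46.5 months.

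The two readings conflict. The Protocol Summary's 2–5 years on drug is a third; it would put first censoring at month 36 or later.

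**2. Model inputs.**
- From the documents: 25 per arm; control response 15% and SD 42%; median OS 16.7 (SD) and 8.9 (PD) months; 2-year enrolment; study length up to 6 years.
- Assumed: the remaining 43% behave as PD; exponential survival within response group; responder median 60 months (range 36–120); combination split 49/25/26% (response/SD/PD); uniform accrual; death the only earlier stop.
- Censoring is at the earlier of last dose + 12 months and the cut-off, compared with the cut-off alone.
- Assumed last dose in months for response/SD/PD: 34/17/17, 34/17/8, 34/17/4 and 24/8/2.

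**3. Deaths captured of 50, cut-off 60 months after first entry (assumed).** A common cut-off gives 38. The window gives 34 under section 5.7's cycles, and 34, 32, 30 and 26 under the four assumed patterns in the order listed. Over responder medians 36–120 the ranges are 24–36 against 35–41. The loss depends on the cut-off chosen:

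| Time on drug | Loss at 36 months | at 48 | at 60 |
|---|---|---|---|
| Section 5.7 cycles + 12 months | 0.3 | 1.8 | about 4 |
| Progressors stop within 2–8 months | about 2–4 (nearer 1 if as late as month 8) | about 4–8 | about 6–12 |

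The larger figures belong to the earliest stopping. At 60 months, log-rank power on these inputs is 31% with a common cut-off, 27% under section 5.7's cycles, and 25, 23, 21 and 18% under the four patterns.

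**4. Kaplan-Meier bias (window minus common cut-off).**
- Month 12: zero in every scenario.
- Month 24, section 5.7 cycles + 12 months: zero in both arms. If the worse-prognosis half stops at 17 cycles, bias appears later: +0.6 to +1.0 points at month 30 and +1.5 to +3.1 at month 36. With halves at random it stays zero.
- Month 24, section 5.7's stated totals less 0.5 month of screening, worse-prognosis half leaving first: +0.8 to +1.0 points (control) and +1.0 to +1.6 (combination). With halves at random it is zero.
- Month 24, control arm, progressors stopping early: +1.3 to +1.6 (34/17/8), +2.9 to +3.4 (34/17/4) and +5.9 to +7.9 (24/8/2).

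**5. Scale.** The standard error of 24-month OS with n = 25 is √(0.335 × 0.665/25) = 9.4 points (control) and √(0.504 × 0.496/25) = 10.0 points (combination). Both exceed every month-24 bias above.

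**The case against.** **Some late deaths would reach the trial.** A reader might infer that no death after the window is ever collected. The documents do not support that. Section 8.3 brings in later deaths judged reasonably related to the study, and sections 5.9.2 and 7.3.5 promise attempts for those lost to follow-up. The first route is selective, however, and a participant who completes the window is not lost. Neither is systematic collection.

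**The window may be a minimum.** The phrase in sections 5.7 and 7.3.7 could be read that way, although its opening words attach to the visit frequency and section 5.9.1 sets an upper limit. The wording needs reconciling, and until then a 12-month stop is the plain reading.

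**The loss partly reflects the comparator.** This stands. The 60-month cut-off is in no section, and on section 5.7's cycles the loss nearly vanishes at 36 months.

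**The schedule might seem to settle time on drug.** It does not. The sixth dose at week 10 plus 24 × 2 weeks gives week 58, or 13.3 months, as one average for all participants. At responder median 60, pattern 34/17/17 averages 13.4 months (control) and 19.3 (combination), 16.3 pooled. Pattern 34/17/4, at 14.3 pooled, is nearer. The zero month-24 bias under 34/17/17 therefore cannot be attributed to the schedule.

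**The later SAP can set a censoring rule.** True, but it cannot recover deaths that were never collected.

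**The consequence is modest.** This also stands: OS is secondary, has no stated power, and sampling error dominates at month 24.

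**Conclusion.** The point holds as a design weakness worth a cheap improvement. Following the plan as written loses OS deaths: about 4 to 12 of 38 at an assumed 60-month cut-off, and far fewer with an earlier cut-off if section 5.7's cycles are right. Kaplan-Meier OS after month 12 may be biased upward. The size is unknown because it turns on when progressors actually stop drug, and section 5.7 contradicts itself on follow-up.

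Three stronger readings should be resisted.
- A reader might infer that OS is substantially inflated. Month-24 bias of up to about 8 points needs progressors to stop within 2 to 8 months, which no section states.
- A reader might infer the opposite, that section 5.7 rules out bias at month 24. That uses only one of its two conflicting readings.
- A reader might infer that log-rank type I error is safe. Different drug durations by arm were not tested under the null, so nothing can be said either way.

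The primary response analysis, OS to month 12 and a control median near 14 months are essentially unaffected. All sizes rest on the assumed exponential survival, responder median, combination split and stopping times.

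**What to change.** - Collect vital status of every randomised participant, including those never treated, by 3-monthly phone or record check to one common cut-off date within the stated study duration. Censor OS only at that date, at true loss to follow-up or at withdrawal of consent. Leave the visit and scan schedule unchanged.
- For participants already past their window, make one record or phone check where consent allows. Section 7.2.4 shows that this version is late-stage, so this may concern about 10 to 24 of 50, some needing tracing.
- Reconcile section 5.7's totals with its one-year follow-up, and the follow-up wording of sections 5.7 and 7.3.7 with section 5.9.1.
- If vital status is not collected, add an inverse-probability-of-censoring sensitivity analysis to the SAP and flag OS estimates beyond the first censoring time. Restricting every OS landmark to month 12 would be more than the evidence requires.

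Cost on the same model, to a 60-month cut-off: about 45 to 113 short contacts in all (45/50 = 0.9 to 113/50 = 2.3 per participant) and one amendment, with no added visits or scans.
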